12.8 Interim Analysis

No interim analysis will be done.

12.9 Measures to Control Bias

12.9.1 Method for Assigning Subjects to Study sequences

The study will be conducted with 6-period and 6 sequences in a cross-over Williams design [37]. A Williams design is an orthogonal Latin squares design with balanced property [38]. On day -1, subjects will be randomized to one of the six study sequences. Details about the randomization process will be included in the Data Management Plan (DMP).

A minimum quota of each sex will be applied to ensure they represent at least 25% of the total study randomized population.

12.9.2 Blinding

This is an open-label study. However, the subjects will be blinded to the randomized sequence. Subjects will be blinded to the products they will receive.

The PMP study statistician and the PMP clinical scientist will be blinded up to the end of the data review process as summarized in Table 11.

 Table 11
 Description of Blinded Study Personnel

Blinded Study Personnel	End of Blinding Period
PMP and CRO Study Statisticians	After the SAP finalization ^a .
PMP Clinical Scientist	After the SAP finalization ^a . Can be actively unblinded when appropriate.

a. As part of the PMP S.A. quality control (QC) activity, a data review will be performed before database lock. Data listings will be reviewed by the CRO and PMP S.A., with no access to the product information for blinded data review team members. Full details will be available in the data review plan.

Confidentiality Statement

12.9.3 Study Significance Level

Not applicable

12.9.4 Multiple Testing Procedures

It is an exploratory study thus no adjustment for multiplicity will be done. When inference will be performed, point estimate and 95% confidence interval (95% CI) will be computed.

12.9.5 Determination of Sample Size and Power Consideration

The sample size is empirically based as there are no considerations for statistical hypothesis.

A total of 24 subjects is expected to be sufficient to obtain a precision of 15% or less on the NP-1: Velo-NP C_{max} ratio.

The precision has been determined using the following geometric coefficient of variation (GCV) and within subjects correlation assumptions for C_{max} :

- For all products the GCV of C_{max} is assumed to be 40%. [1]
- The correlation within subjects on log-transformed data is assumed to be 0.7. It has been derived as the correlation that would explain the width of the confidence interval of the C_{max} difference between the Zyn and Velo-NP product, as compared to the confidence interval of the C_{max} of Zyn-NP and Velo-NP product as described in [16].

The precision has been determined using 10,000 simulations performed with SAS®.

Confidentiality Statement

13.1.3 Other Responsibilities

Confidentiality Statement

Philip Morris Products S.A.	Clinical Study Protocol	Confidential
P5-PK-01-EXP	2.0, Approved	Page 87 of 98
P.1. 1. 01/0 0017500		

All duties and responsibilities transferred by the Sponsor to the above listed CROs will be defined in an agreement signed between the relevant two parties.

Any SAEs or pregnancies will be handled as described in section 8.3.

Details of the laboratories conducting the clinical safety laboratory services and bioanalyses are shown in Appendix B.

13.2 Subject Recruitment

Subjects will be recruited from the volunteers' database maintained by the CRO. This database contains a pool of volunteers that are contacted whenever necessary to enroll subjects in a new study. Before the start of the new study, the Investigator and other relevant staff discuss with the volunteers' recruiter the study recruitment needs and specific requirements. On the basis of this information, the volunteers' recruiter queries the database, contacts potential volunteers to propose the study and evaluate their interest and availability. In addition to the volunteer's database, IEC-approved advertisement will be used. New subjects often call or email the CRO asking to become a research volunteer, after hearing of the clinical site activities from other volunteers or friends or after checking the company web site. The CRO and its clinical site have detailed SOPs on the recruitment process.

13.3 Subject Confidentiality

All information obtained during the conduct of the study with respect to the subjects' state of health will be regarded as confidential. A statement to this effect will be written in the information provided to the subject. An agreement to disclose any such information will be obtained from the subject in writing and signed by the subject, in compliance with all local and national data protection and privacy legislation.

The name of the subjects participating in this study will be kept confidential. Subjects will be identifiable by the Sponsor (or Sponsor's authorized representative) on CRFs and other documents by their subject (or randomization) number/code, sex, and age, but not by name, initial, or any other details relating to identifiable person (e.g., address, social security number, medical chart number, etc.). The assignment of a subject number/code for subject identification will be based on the appropriate data protection rules.

Any documents that allow full identification of the subject (e.g., the subject's signed ICF) must be maintained in confidence by the Investigator. If any document relating to this study shows a subject's name or any other details relating to an identifiable person (e.g., address, social security number, medical chart number, etc.), the name or other identifiable details must be obscured before a copy of that document is supplied to the Sponsor or the Sponsor's authorized representative.

Confidentiality Statement

13.4 Access to Source Documentation

Subjects will be informed that, during the study, the Sponsor, any authorized representatives of the Sponsor, IEC/IRB or regulatory authorities may inspect their medical records and source documentation to verify the information collected and ensure that all personal information made available for inspection is handled in the strictest confidence and in accordance with national and local data protection and privacy legislation.

The Investigator and all investigational site staff involved with the study must permit direct access to source data/documents for study related monitoring, audits, IEC/IRB review and regulatory inspection(s).

13.5 Record Retention

All records of data, source data and source documents (original records or certified copies), in any form (including, but not limited to, written, electronic, magnetic, optical records and scans and ECGs) that describe or record the methods, conduct, and/or results of the study, the factors affecting the study and the actions taken will be maintained by the investigational site for the study, as required by ICH GCP [1] and any other applicable local or national regulations.

Essential study documents/records, which individually and collectively permit evaluation of the conduct of a study and the quality of the data produced, are described in section 8 of the ICH GCP Guideline [1].

Essential documents must be retained by the Investigator for a minimum of:

• At least 15 years after completion or discontinuation of the study.

However, these documents should be retained for a longer period if required by the applicable regulatory requirements or by agreement with the Sponsor.

Examples of essential records/documents include, but are not limited to:

- Signed informed consent documents for all subjects and master ICF.
- Subject identification code list, Screening log and Enrollment log (if applicable).
- Record of all communications between the Investigator and the IEC/IRB, composition of the IEC/IRB.
- Record of all communications/contact between the Investigator, the Sponsor, and its authorized representatives.
- List of sub-Investigators and other appropriately qualified persons to whom the Investigator has delegated significant study-related duties, together with their roles in the study, CVs, and their signatures.
- CRFs, study specific questionnaires (and associated data/scoring).

Confidentiality Statement

Philip Morris Products S.A.	Clinical Study Protocol	Confidential
P5-PK-01-EXP	2.0, Approved	Page 89 of 98
D-1-4-14- OMC 0017599	P	

- AE reports and details of follow-up investigations, details of concomitant medication.
- All other source documents (e.g., ECGs, consultation reports, physical examination and laboratory records) or any electronically captured study source data.
- Clinical laboratory reports, laboratory normal ranges.
- Original medical/hospital records, if applicable (the medical files of study subjects must be retained in accordance with local legislation and in accordance with the maximum period of time permitted by the hospital or study site).
- Record of any body fluids or tissue samples collected and retained.
- IP Accountability Logs, dispensing records.
- Information regarding subjects' discontinuation and any follow-up.

It is the responsibility of the Sponsor to inform the Investigator/study site as to when these documents no longer need to be retained.

The Investigator/study site must take measures to prevent accidental or premature destruction of these documents.

If an Investigator wishes to assign the study records to another party or move them to another location, the Sponsor must be notified in advance. The Investigator must obtain written approval from the Sponsor before destruction of any records. Normally, these records will be held in the Investigator's archives. If an Investigator is unable to meet this obligation, they must ask the Sponsor for permission to make alternative arrangements. Details of these arrangements must be documented.

The Sponsor or Sponsor's authorized representative will maintain documentation relating to the study as long as the IP is on the market, and/or for 15 years after the CSR has been finalized.

13.6 Clinical Study Report

The Sponsor must ensure that a CSR for this study is prepared regardless of whether the study is completed or prematurely terminated.

The CSR will be written based on standards of the ICH Guideline for the "Structure and Content of Clinical Study Reports" [39]. In certain circumstances, an abbreviated CSR may be acceptable. Submission of the CSR to the IEC/IRB will be complied with as requested by local requirements.

13.7 Financial Disclosure

Investigators and any designees are required to provide financial disclosure information to the Sponsor. In addition, the Investigators and designees must provide the Sponsor with a

Confidentiality Statement

Philip Morris Products S.A.	Clinical Study Protocol	Confidential
P5-PK-01-EXP	2.0, Approved	Page 90 of 98
Related to QMS-0017588		Document ID: VV-TMF-00821

Document ID: VV-TMF-00821

commitment to promptly update this information if any relevant changes occur during the study and for one year following the completion of the study.

13.8 Publication and Disclosure Policy

This document contains information that is confidential and proprietary to the Sponsor. This information is being provided solely for the purpose of evaluation and/or conducting this study for the Sponsor. Disclosure of the content of this document is allowed only to study personnel, IEC/IRB, or duly authorized representatives of regulatory agencies for this purpose under the condition that confidentiality is maintained. The contents of this document may not be used in any other study, disclosed to any other person or entity without the prior written permission of the Sponsor. The foregoing shall not apply to disclosure required by any regulations; however, prompt notice must be given to the Sponsor prior to any such disclosure.

The study will be registered and published in a WHO primary register or at www.clinicaltrials.gov.

APPENDIX A SCHEDULE OF EVENTS

Study Day	Day -22 to -2 Screening	Day -1 Admission	Day 1	Day 2	Day 3 Discharge/ Early termination	Day 4 to 6 Safety Follow-Up
Informed consent	•					
Information on the risks of smoking/advice on smoking cessation and debriefing on Nicotine pouch 1.0	•	•			● P	
Inclusion/exclusion criteria ^a	•	•				
Nicotine/Tobacco product use history	•	•				
Demographics ^b	•					
Medical history, concomitant diseases	•	●C	● C	● C	●c	
Prior medication/ Concomitant medication ^d	•	•	•	•	• P	• q
Physical examination	•	•			• P	
Body height, weight and related BMI	•					
Vital signs ^e	•	•	•	•	• p	

Confidentiality Statement

Philip Morris Products S.A.	Clinical Study Protocol	Confidential
P5-PK-01-EXP	2.0, Approved	Page 95 of 98

Document ID: VV-TMF-00821

Study Day	Day -22 to -2 Screening	Day -1 Admission	Day 1	Day 2	Day 3 Discharge/ Early termination	Day 4 to 6 Safety Follow-Up
ECG ^f	•	•			• P	
Spirometry	•					
Blood and urine sample for hematology, clinical chemistry, urine analysis safety panel ^g	•	•			• P	
Blood sample for serology ^h	•					
Urine sample for drug test	•	•				
Urine sample for cotinine test	•	•				
Urine pregnancy test (females)	•	•			• P	
Blood sample for trans -3'- hydroxycotinine and cotinine (CYP2A6 activity) in plasma ⁱ		•				
Fagerström Test for Nicotine Dependence	•					
NP-1 product test ^j		•				
Enrollment		•				
Randomization		•				
30 min product use periods in the morning and in the afternoon			•	•	•	
Blood sample collection for plasma nicotine ¹			•	•	•	

Confidentiality Statement

Philip Morris Products S.A.	Clinical Study Protocol	Confidential
P5-PK-01-EXP	2.0. Approved	Page 96 of 98

Document ID: VV-TMF-00821

Study Day	Day -22 to -2 Screening	Day -1 Admission	Day 1	Day 2	Day 3 Discharge/ Early termination	Day 4 to 6 Safety Follow-Up
Product Evaluation Scale (PES) ^m			•	•	•	
VAS craving assessment ⁿ			•	•	•	
VAS liking (in-the-moment) assessment ⁿ			•	•	•	
VAS liking (overall) assessment ⁿ			•	•	•	
VAS satisfaction assessment ⁿ			•	•	•	
VAS intention-to-use-again assessment ⁿ			•	•	•	
Sensory questionnaire ^m			•	•	•	
AE/SAE recording	•	•	•	•	• P	•
Product events		•	•	•	• P	
Support during periods of abstinence from any tobacco and nicotine containing products (as required)		•	•	•	•	
Collection of used products °			•	•	•	

Abbreviations: AE = Adverse event; BMI = Body mass index; ECG = Electrocardiogram; SAE = Serious adverse event

a. Prior to enrollment at Admission on Day -1, the following inclusion and exclusion criteria will be re-checked: Inclusion Criteria: (4) Subject has smoked ≥ 10 commercially available cigarettes per day for 4 weeks prior to Screening Visit and Admission. Smoking status will be verified based on a urinary cotinine test (cotinine ≥ 500 ng/mL), (5) Subject does not plan to quit smoking or using other nicotine/tobacco-containing products in the next 3 months. Exclusion criteria: (10) Subject has a positive urine drug including alcohol test, (15) For women only: subject is pregnant (does not have negative pregnancy tests at Screening Visit and Admission) or is breastfeeding, (16) For women of childbearing potential only: subject does not agree to use an acceptable method of effective contraception, (17) Use of estrogen-containing hormonal contraception or hormone replacement therapy.

Confidentiality Statement

Philip Morris Products S.A.	Clinical Study Protocol	Confidential
P5-PK-01-EXP	2.0, Approved	Page 97 of 98

Document ID: VV-TMF-00821

The following eligibility criteria will only be checked at Admission: (7) Subject has received medication within 14 days or within 5 half-lives of the drug prior to Admission, whichever is longer, which has an impact on CYP2A6 activity.

- b. Sex, date of birth/age, race and ethnicity.
- c. Concomitant disease status.
- d. All medication taken within 4 weeks prior to the Screening Visit will be documented. Prior medication which has an impact on CYP2A6 activity taken within 14 days or within 5 half-lives of the drug (whichever is longer) prior to Day -1 is an exclusion criterion.
- e. Systolic and diastolic blood pressure, pulse rate and respiratory rate. On Day 1 to Day 3 in the morning, vital signs will be assessed prior to T_{0M} .
- f. At Screening an ECG will be performed after signed ICF and at least 1 hour after smoking cigarettes, on Day -1 an ECG will be performed prior to enrollment, on Day 3 an ECG will be performed 60 minutes \pm 10 minutes after T₀.
- g. Blood samples should be taken in the morning of the Screening visit, Admission (Day -1) and Discharge (Day 3) or at Early termination. Subjects should have fasted for at least 10 hours prior to safety laboratory assessments except at the Screening visit and Early termination where non-fasting samples will be used.
- h. Tests for hepatitis B (HbsAg), hepatitis C (HCV antibody) virus and human immunodeficiency virus (anti-HIV1/2) will be performed at the Screening Visit.
- i. Sample taken prior to NP-1 product test.
- j. On Day -1, after enrollment, subjects will perform a product test using NP-1 for 30 minutes (± 1 minute).
- k. On Day 1 to Day 3 in the morning and in the afternoon, subjects will use one product for 30 minutes (± 1 minute) according to the randomized product use sequence.
- 1. On Day 1 to Day 3, 24 blood samples will be taken for determination of nicotine concentration: one blood sample will be taken prior to the start of product use in the morning (T_{0A}) 5 minutes \pm 1 minute (T-1). Thereafter in relation to T_{0A}, blood will be drawn at the following time points: T1 after 5 minutes \pm 1 minute, T2 after 10 minutes \pm 1 minute, T3 after 15 minutes \pm 1 minute, T4 after 20 minutes \pm 1 minute, T5 after 25 minutes \pm 1 minute, T6 after 30 minutes \pm 1 minute, T7 after 35 minutes \pm 1 minute, T8 after 40 minutes \pm 1 minute, T9 after 1 hour \pm 5 minutes, T10 after 3 hours \pm 5 minutes, T11 after 6 hours \pm 5 minutes. On Day 2, 2 additional blood samples will be taken for determination of the terminal elimination half-life (t_{1/2z}). Blood samples will be taken in relation to T_{0A} from Day 2 at the following time points: T12 after 8 hours \pm 5 minutes and T22 after 12 hours \pm 5 minutes.
- m. On Day 1 to Day 3 in the morning and in the afternoon, the PES and the Sensory questionnaire will be answered at T9 after 1 hour \pm 5 minutes, after T_{0M} and T_{0A}.
- n. On Day 1 to Day 3 in the morning and in the afternoon, VAS craving, VAS liking (in the moment) and VAS satisfaction assessments at: Within 15 minutes prior to T_{0M} and T_{0A} (VAS craving only), and at T1 after 5 minutes ± 1 minute, T2 after 10 minutes ± 1 minute, T3 after 15 minutes ± 1 minute, T4 after 20 minutes ± 1 minute, T5 after 25 minutes ± 1 minute, T6 after 30 minutes ± 1 minute, T7 after 35 minutes ± 1 minute, T8 after 40 minutes ± 1 minute, T9 after 1 hour ± 5 minutes, T10 after 3 hours ± 5 minutes (VAS craving and VAS satisfaction only), T11 after 6 hours ± 5 minutes (VAS craving and VAS satisfaction only), T11 after 6 hours ± 5 minutes, after T_{0M} and T_{0A}. On Day 1 to Day 3 in the morning and in the afternoon, VAS liking (overall) assessment at: T10 after 3 hours ± 5 minutes, after T_{0M} and T_{0A}. On Day 1 to Day 3 in the afternoon, VAS intention to use again assessment at: T6 after 30 minutes ± 1 minute, and T10 after 3 hours ± 5 minutes, after T_{0M} and T_{0A}.
- o. On Day 1 to Day 3 in the morning and in the afternoon, used product will be collected for analysis of residual nicotine.
- p. Early termination assessments to be conducted in subjects who withdraw consent / are discontinued from the study.
- q. Only medication administered as treatment for an adverse event

Confidentiality Statement

PHILIP MORRIS PRODUCTS S.A.

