2.3.3 Anticipated Foreseeable Risks due to Investigational Product

By product design, NP 1.0 variants are free from the majority of HPHCs associated with heating or burning tobacco, except nicotine.

Confidentiality Statement

Philip Morris Products S.A.	Clinical Study Protocol	Confidential
P5-PK-01-EXP	2.0, Approved	Page 29 of 98
D 1 . 1. 01/2 001/2 000		

Due to sensorial and technological differences between NP 1.0 versus cigarettes and the confinement setting, subjects may modify their nicotine uptake.

An adult smoker using NP 1.0 may experience:

- Transient nicotine withdrawal symptoms (e.g., urge to smoke, irritability, anxiety feelings, restlessness, and difficulty to concentrate) similar to cravings observed during smoking cessation
- Transient symptoms suggesting mild nicotine overdose such as stimulatory effects on sympathetic tone (increased blood pressure, increased heart rate), central nervous system (tremor, blunting of emotions, and decreased ability to concentrate), gastric acid secretion, and vomiting.

Support during periods of abstinence from any tobacco and nicotine containing products will be provided.

Further risk mitigation will include:

- Using commonly accepted research and scientific standards (e.g., blood samples not to exceed blood donation standards)
- Medical supervision of all study subjects with follow-up of those who have experienced AEs/serious adverse events (SAEs)

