6.6 Restrictions

6.6.1 Smoking Restrictions

During the Screening period, subjects will be allowed to use any nicotine/tobaccocontaining products according to their usual habits except during the procedures of the Screening Visit (section 9.1). Spirometry assessment at Screening will be performed 1 hour after stopping smoking (section 9.1).

From Admission (Day -1) to Discharge (Day 3) or early termination, use of any nicotine/tobacco containing products, except use as per study design of the allocated product will not be permitted.

A nicotine washout period of at least 8 hours should be respected before T_{0M} and T_{0A} of NP use at Day 1 to Day 3.

Confidentiality Statement

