7.4.7 Electrocardiogram

A standard 12-lead ECG will be recorded after the subject has rested for at least 10 minutes in supine position.

All ECGs will be reviewed on an ongoing basis by the Investigator or designee. The following parameters will be documented: heart rate, PR interval, QRS interval, QT interval, and QTc interval corrected according to Fridericia's formula.

For those results outside of the normal range, the Investigator will determine appropriate follow-up including reporting of any AEs.

Any printouts of ECGs on thermo-sensitive paper must be photocopied and stapled together for inclusion in the source documents

Confidentiality Statement

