8.9 Electrocardiogram

An ECG will be recorded at Screening, Admission (Day -1), and at Day 3. If applicable, an early termination assessment will be performed.

The ECG testing will be performed as per the investigational site standard practice. A standard 12-lead ECG will be recorded after the subject has rested for at least 10 minutes in supine position.

Statistical Analysis Plan Number CA36095

The following parameters will be documented: heart rate, PR interval, QRS interval, QT interval, and QTc interval, corrected by the ECG device according to Fridericia's formula [QTcF]. Every ECG has to be assessed as normal, abnormal – not clinically significant, or abnormal – clinically significant.

Descriptive statistics will be presented for each ECG parameter by study day. Change from baseline will be summarized in a similar manner. Baseline is defined as the result closest and prior to the first product administration, which may include unscheduled or recheck results. This will typically be the result collected at Admission (Day -1). Post product use unscheduled events or rechecks will not be included in summaries. Similarly, early termination results will not be included in summaries. QTcF values that are > 450 msec or increase from baseline > 30 msec will be flagged in the data listing.

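### The Day -1 ECG, normally the analysis baseline, carries no minimum interval since the last cigarette, although the Screening ECG does

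*Protocol*

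**What the plan says.** Appendix A, note f, sets the ECG conditions. For Screening: "At Screening an ECG will be performed after signed ICF and at least 1 hour after smoking cigarettes". Where the sentence passes from Screening to Admission it reads "at least 1 hour after smoking cigarettes, on Day -1 an ECG will be performed prior to enrollment", with no smoking interval for the Day -1 recording. For Day 3 it places the recording 60 ± 10 minutes after T0.

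SAP 8.9 fixes the reference value: "Baseline is defined as the result closest and prior to the first product administration". It then adds "This will typically be the result collected at Admission (Day -1"), so the unconditioned recording is normally the baseline.

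The general procedure in Protocol 7.4.7 concerns posture and rest only: "A standard 12-lead ECG will be recorded after the subject has rested for at least 10 minutes in supine position". Table 5 (Section 9.2) lists the ECG among the procedures before enrollment, with the NP-1 product test later the same day, and adds no nicotine condition. SAP Table 4.3 gives the Day -1 ECG window as not applicable.

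Two sections bear on when smoking stops. Section 6.6.1 opens its ban with "From Admission (Day -1) to Discharge (Day 3) or early termination, use of any nicotine/tobacco containing products" and exempts only the allocated product. Section 6.2.1 places the abstinence instruction after the product test.

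**The concern.** The condition protects the ECG that is normally not the baseline and omits the one that is. Comparable measurements are protected: vital signs need at least 15 minutes without nicotine (7.4.5), and spirometry needs 1 hour after smoking (6.6.1, 7.4.6). The baseline for vital signs is typically the reading before the first morning use on Day 1 (SAP 8.8), which follows at least 8 hours of abstinence. The ECG baseline has nothing equivalent.

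Change from baseline in heart rate, PR, QRS, QT and QTcF is a named endpoint under Objective 3. Among the expected nicotine effects, Protocol 2.3.3 lists "stimulatory effects on sympathetic tone (increased blood pressure, increased heart rate". A baseline heart rate raised by a recent cigarette would make the Day 3 change look smaller than it is. Day 3 is the only scheduled ECG after baseline, so no later reading dilutes the problem.

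**Working it through.** The plan states no figure to reproduce here. The check compares passages and adds two short calculations for scale.

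**1. Smoking interval by ECG**

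| ECG | Smoking interval stated | Role |
|---|---|---|
| Screening | at least 1 hour (note f) | eligibility; not normally the baseline |
| Day -1 | none (note f, 7.4.7, Table 5, SAP 8.9, SAP Table 4.3) | normally the baseline (SAP 8.9) |
| Day 3 | 60 ± 10 minutes after T0 of pouch use (note f) | the change is computed here |

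**2. Does the general smoking ban close the gap?** Free smoking is granted for the Screening period, which ends on Day -2 (6.2, 6.6.1, 9.1). There are three ways to read what follows:

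- If Admission (Day -1) means the whole calendar day, smoking before the ECG is already barred.
- If it means arrival at the site, a cigarette on site is a deviation, but one smoked just before arrival is not.
- If Section 6.2.1 governs, abstinence starts only after the product test, hence after the ECG.

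The documents do not say which applies. Eligible subjects smoke at least 10 cigarettes a day (inclusion criterion 4), so a recent cigarette on arrival is plausible. The 8-hour washout applies before product use on Days 1 to 3, not before the Day -1 ECG. The Day -1 product use history covers the past 4 weeks (7.8.2), and Table 5 does not schedule recording the time of the last cigarette.

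**3. Nicotine remaining after a cigarette (scale only).** Input: initial half-life 1.35 h = 81 minutes (Protocol 4.2). Formula: fraction remaining = 0.5^(t/81), ignoring absorption lag and the terminal phase.

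- t = 10 min (the minimum supine rest): 0.5^(10/81) = 0.918
- t = 15 min (the vital-signs interval): 0.5^(15/81) = 0.880
- t = 30 min: 0.5^(30/81) = 0.774
- t = 60 min (the Screening ECG interval): 0.5^(60/81) = 0.598

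The ratio of 10 to 60 minutes is 0.918/0.598, about 1.5. The supine rest alone therefore removes little nicotine. The 1-hour interval removes more, but about 60% remains. These are nicotine fractions, not ECG effects.

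**4. Effect on mean change in heart rate.** If a share p of subjects has baseline raised by x, the mean change shifts by −p·x. The documents give neither p nor x. The values below are assumptions, in beats per minute:

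| p | x = 5 | x = 10 | x = 15 |
|---|---|---|---|
| 0.25 | −1.25 | −2.5 | −3.75 |
| 0.50 | −2.5 | −5 | −7.5 |
| 1.00 | −5 | −10 | −15 |

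The shift does not depend on sample size, so 24 subjects or more would not average it out. The last row requires every subject to have smoked shortly before the ECG.

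**The case against.** The strongest objection is Section 6.6.1. It bars nicotine from Admission (Day -1), and on its widest reading the gap disappears. The 10 minutes of supine rest also rules out a recording immediately after a cigarette. This narrows the problem mainly to a cigarette smoked before arrival, less than 1 hour before the ECG. It does not close it, because no starting time is given and 6.2.1 reads differently.

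A reader might infer that every subject's baseline is inflated and that mean change is biased by the full 5 to 15 beats per minute. The documents do not support that: only subjects who smoked shortly before the ECG are affected, no share is given, 6.6.1 argues against a share of 100%, and the range itself is an assumption.

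A reader might also infer that the baseline hides a product effect. This ECG could not isolate one in any case. There is a single Day 3 recording, taken after the product test and several different pouches, with no unexposed control. SAP 8.9 summarises by study day. Protocol 12.7 adds reporting by sequence, but that leaves about 24/6 = 4 subjects in each. Nor is the comparison one of recent smoking against a nicotine-free state, since the Day 3 ECG follows pouch use.

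The rest of the objection concerns consequence, and it stands. QTcF is already rate-corrected, its flag only marks a listing, and the 450 msec arm of the flag does not use baseline. The Screening ECG, with its 1-hour condition, remains available in the listings.

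**Conclusion.** The point holds as a gap in how the baseline is standardised. The 1-hour interval is written for the Screening ECG, the baseline is normally the Day -1 ECG, and no section states a smoking interval for it. The start of abstinence on Day -1 is also inconsistent between 6.2.1 and 6.6.1.

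The size is p times x for mean heart-rate change, towards a smaller change, and cannot be fixed from the documents. The conclusion assumes that some subjects smoke within the hour before the recording, which the plan permits on at least one reading of 6.6.1. For QTcF even the direction is unknown. The consequence is confined to descriptive ECG safety summaries and one listing flag in an exploratory study; no PK or PD result depends on it. This is an inexpensive improvement, not a threat to the main objective.

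**What to change.** - In Appendix A note f, and again in Section 7.4.7, apply the existing 1-hour measurement condition to the Day -1 ECG.
- Record the time of last nicotine or tobacco use before that ECG, so that recordings made earlier than 1 hour can be flagged in the listing.
- Reconcile Sections 6.2.1 and 6.6.1 on when abstinence starts on Day -1. This review takes no position on which is right.

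The cost is one line of protocol text (repeated in 7.4.7), one CRF field and a slightly longer admission; the other pre-enrollment procedures in Table 5 can fill the hour. The interval lessens the influence of recent smoking but does not abolish it, so the recorded time remains useful even when the condition is met.
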